a) The study proponent has performed a propensity score matched analysis of participants undergoing elective open surgical intervention for PAD.²⁸ The primary objective of this study was to assess the independent effects of nadir postoperative Hb (nHb) level and transfusion on a composite outcome of death or acute coronary syndrome (ACS) up to 30 days postoperatively. Secondary endpoints included perioperative wound and respiratory complications; and death or adverse cardiac events during an average follow-up of 24 months. A total of 1074 PAD-related operations were examined. In light of reports indicating a harmful effect of blood transfusion on mortality and cardiac outcomes, the analysis was adjusted for units of PRBCs transfused prior to the occurrence of any of the events that consisted of components of the composite outcome. Level of statistical significance in this study was set at alpha 0.0125 to account for the four comparisons performed when assessing the primary endpoint (two exposures tested against two individual outcomes).

TABLE 1: Effect of Nadir Hb and Units of Blood Transfused on a Composite Endpoint of Death, or ACS

Variable	Odds Ratio	Standard Error	P-Value	95% Confidence Interval
Nadir Hb < 10gm/dl	Reference	Reference	Reference	Reference
Nadir Hb ≥ 10gm/dl	0.62	0.17	0.120	0.33-1.14
Transfusion units	1.11	0.05	0.025	1.01-1.22

Univariate analysis in this study demonstrated a relative protective but not statistically significant effect of nHb ≥ 10 gm/dl on the composite endpoint of death or ACS (OR: 0.68, 95% CI: 0.54 to 1.19, p=0.12). On the multivariable model that included as predictors both nHb and units of blood transfused, nHb ≥ 10 gm/dl was again seen to have a relative protective effect on the composite endpoint, although again this difference did not reach statistical significance. (OR:

Transfusion Trigger after Operations in High Cardiac Risk Patients (TOP)

[figure not shown]
5

Version Number: 11 Date: 12/18/2024

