Subject demographics and pre-surgical baseline characteristics will be summarized for each intervention group and for all participants (ITT and mITT). The subject demographics such as age, race, gender, ethnicity etc. and baseline test results such as Hb, albumin, troponin, creatinine, EKG, SBP/DBP, BMI, RCRI etc. will be analyzed. For continuous variables, the sample size, mean, median, SD, minimum, and maximum values will be calculated and tested either by Student t or Wilcoxon test depending on data distributions. For categorical variables, the number and percentage of participants by the intervention group will be tabulated and tested using Pearson chi-square test.

Disposition status

Subject disposition will be summarized for the ITT and mITT populations. The number and percentage of participants who completed or discontinued prematurely from the study by intervention group will be tabulated and tested using Pearson chi-square test. The number and percentage of participants who discontinued for each reason will be presented for each intervention group. The number and percentage of participants who completed or discontinued prematurely in each intervention group will also be displayed graphically.

Adherence

Participants who change transfusion strategy after randomization or have protocol violations will be identified as non-adherence to the intervention (ITT and mITT). The number and percentage of non-adherence participants will be summarized by intervention group and tested using Pearson chi-square test.

Age of blood in relation to 90 day composite endpoint, wound infection, and pneumonia

Analyses will be conducted of the associations between characteristics of transfused blood and three outcome measures (90 day composite endpoint, wound infection, and pneumonia). Current data collection plans call for blood expiration dates and the age of each unit of blood transfused will be calculated. Logistic regression models will be fitted to test for association between these outcomes and age of blood transfused (entered in different models as oldest unit transfused or as mean age of all units transfused). The analyses will be adjusted for age, RCRI, nadir Hb, site, and the transfusion intervention. The test for differences of these outcomes will be conducted at an α -level of 0.01. The analyses will be done on the ITT, mITT, No-Recent-Transfusion, Completers, and Per Protocol populations.

Time-to-event analysis for primary and major secondary endpoints

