7.4. Other Analyses

Age of blood in relation to 90-day composite endpoint, wound infection, and pneumonia

Analyses will be conducted of the associations between characteristics of transfused blood and three outcome measures: 90-day composite endpoint (Tables 24a-e), wound infection (Tables 25a-e), and pneumonia (Tables 26a-e). Current data collection plans call for blood expiration dates and the age of each unit of blood transfused will be calculated. Logistic regression models will be fitted to test for association between these outcomes and age of blood transfused (entered in different models as oldest unit transfused or as mean age of all units transfused). The analyses will be adjusted for baseline age, RCRI, nadir Hb, and the transfusion intervention. The test for differences of these outcomes will be conducted at an α -level of 0.05 for the primary outcome and 0.01 for wound infection and pneumonia. The analyses will be done in the ITT, mITT, No-Recent-Transfusion, Completers, and Per Protocol populations.

Time-to-event analysis for primary and major secondary endpoints

Survival analysis techniques will be used to analyze the time-to-event data for the primary and major secondary endpoints. Kaplan-Meier method will be used to estimate the survival (not experiencing event) over time in the two intervention groups and a log-rank test

will be used to compare the survival functions in the two groups for the primary endpoint and the secondary endpoints using PROC LIFETEST. Cox's Proportional Hazards models will be used to test the effect of the intervention on the time until endpoint events adjusted for age, RCRI, and nadir Hb, as described in the primary endpoint (Tables 27a-e, with an α -level of 0.05), and secondary endpoint (Tables 28a-e, with an α -level of 0.01) analyses using PROC PHREG. The analyses will be done in the ITT, mITT, No-Recent-Transfusion, Completers, and Per Protocol populations.

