Outcomes		Liberal	Restrictive	All Subjects	χ^2	p-Value
		(N =)	(N =)	(N=)		
90-day all-cause mortality	Present					
	Absent					
	Total					
90-day MI	Present					
	Absent					
	Total					
90-day coronary revascularization	Present					
	Absent					
	Total					
90-day stroke	Present					
	Absent					
	Total					
90-day acute renal failure	Present					
	Absent					
	Total					

Table 23a-e. Transfusion Related Individual Components of the Composite Endpoint, Logistic Regression (ITT, mITT, No-Recent-Transfusion, Completers, Per-Protocol)

	Outcomes	Coefficients	SE	p-Value	OR	OR 99% C.I.	
						Lower	Upper
90-day all-cause mortality	Liberal vs Restrictive						
	Age						
	RCRI						
	1						
	2						
	3						
	4						
	Nadir Hb						
	Transfusion and Age						
	Liberal vs Restrictive						
90-day MI	Age						
	RCRI						
	1						
	2						
	3						
	4						
	Nadir Hb						
	Liberal vs Restrictive						
	Age						
	RCRI						
90-day coronary revascularization	1						
	2						
	3						
	4						
	Nadir Hb						
	Liberal vs Restrictive						
	Age						
	RCRI						
	1						
	2						
90-day stroke	3						
	4						
	Nadir Hb						
	Liberal vs Restrictive						
	Age						
	RCRI						
	1						
	2						
	3						
	4						

	Outcomes	Coefficients	SE	p-Value	OR	OR 99% C.I.	
						Lower	Upper
90-day acute renal failure	Liberal vs Restrictive						
	Age						
	RCRI						
	1						
	2						
	3						
4							
	Nadir Hb						

Tables 24a-e. Effect of Age of Blood Transfused on Primary Outcome (ITT, mITT, No-Recent-Transfusion, Completers, Per-Protocol)

Factors	Coefficients	p-Values (Wald test)	OR (95% C.I.)
Using oldest unit transfused			
Age of Blood Transfused			
Liberal vs Restrictive			
Baseline Age of Participant			
RCRI			
1			
2			
3			
4			
Nadir Hb			
Using mean age of all the units transfused			
Age of Blood Transfused			
Liberal vs Restrictive			
Baseline Age of Participant			
RCRI			
1			
2			

3			
4			
Nadir Hb			

Tables 25a-e. Effect of Age of Blood Transfused on 90-day Wound Infection (ITT, mITT, No-Recent-Transfusion, Completers, Per-Protocol)

Factors	Coefficients	p-Values (Wald test)	OR (99% C.I.)
Using oldest unit transfused			
Age of Blood Transfused			
Liberal vs Restrictive			
Baseline Age of Participant			
RCRI			
1			
2			
3			
4			
Nadir Hb			
Using mean age of all the units transfused			
Age of Blood Transfused			
Liberal vs Restrictive			
Baseline Age of Participant			
RCRI			
1			
2			
3			
4			
Nadir Hb			

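### The oldest-unit age-of-blood models omit the number of units transfused, so they can report dose as a storage effect; the alpha for the composite also differs between protocol and SAP

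*SAP*

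**What the plan says.** SAP 7.4 fits logistic models for three outcomes (90-day composite, wound infection, pneumonia). Storage age is "entered in different models as oldest unit transfused or as mean age of all units transfused". On covariates it says: "The analyses will be adjusted for baseline age, RCRI, nadir Hb, and the transfusion intervention". Protocol XVI.E.5 has the same two exposure definitions and says: "The analyses will be adjusted for age, RCRI, nadir Hb, site, and the transfusion intervention". The lists differ on site, which does not bear on this point. Number of units is in neither list, and the shells for Tables 24–26 in SAP Appendix 5 have no row for it.

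On significance, the protocol says of all three outcomes: "The test for differences of these outcomes will be conducted at an α -level of 0.01". The SAP uses "0.05 for the primary outcome and 0.01 for wound infection and pneumonia". The shell headed "Tables 24a-e. Effect of Age of Blood Transfused on Primary Outcome" carries 95% intervals to match; Tables 25 and 26 carry 99% intervals. Protocol XVI.H says that the SAP will state where it departs from the protocol. Section 7.4 states no departure.

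Protocol X has the number of transfusions recorded before, during and after the operation, and SAP Appendix 2 has a transfusion record (Form 4).

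**The concern.** The maximum of k values rises with k even when all values come from one distribution. A participant given four units will usually have an older oldest unit than one given a single unit, with no difference in how blood was stored or issued. If participants who receive more units also do worse, a model with oldest-unit age and no term for units credits part of that association to storage.

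The documents make a link between units and outcome plausible. Protocol II, Table 1 ("Effect of Nadir Hb and Units of Blood Transfused on a Composite Endpoint of Death, or ACS") gives an odds ratio of 1.11 per unit with nadir Hb in the model. Protocol I cites a cardiac-surgery trial in which units transfused predicted mortality and several complications, infectious ones included. Adjusting for arm does not remove dose, because units vary within an arm: Protocol X sets one, two or three units in the liberal arm by Hb level.

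At stake is a published statement that older blood is associated with worse outcome when the signal is volume transfused. For the composite, the unexplained difference in alpha adds doubt about which result would count as significant.

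**Working it through.** **Plan's own figure.** The documents give no power or sample size for these models. The only plan figure used is the trial size. At 30% vs 22.5%, two-sided 5%, 90% power, the two-proportion formula without continuity correction gives 722 per arm, or 1444; 1444/0.95 = 1520. This reproduces.

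**Oldest unit against number of units.** Assume storage ages independent and uniform over 1–42 days (not in the documents). Then E[oldest of k] = 1 + 41·k/(k+1):

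| Units k | 1 | 2 | 3 | 4 | 6 |
|---|---|---|---|---|---|
| Expected oldest (days) | 21.5 | 28.3 | 31.8 | 33.8 | 36.1 |
| Expected mean (days) | 21.5 | 21.5 | 21.5 | 21.5 | 21.5 |

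The mean does not move with k. That is why only the oldest-unit models are exposed.

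**False-positive rate with no storage effect.** Inputs from the documents: N = 1520; the SAP 7.4 covariates; odds ratio per unit 1.11 with 95% CI 1.01–1.22 (Protocol II, Table 1). Assumed: mean units 2.2 (liberal) and 0.5 (restrictive), overdispersed and rising with an unmeasured severity that also lowers nadir Hb; storage ages as above. The outcome depends on age, RCRI, nadir Hb and units, not on storage. Each model has arm, age, RCRI class, nadir Hb and storage age, and is fitted to transfused participants (about 830). There were 600 runs per row. Entries are percent rejected at nominal 5% / 1%.

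| OR per unit | Oldest, SAP covariates | Oldest + units | Mean age, SAP covariates |
|---|---|---|---|
| 1.00 | 5.7 / 1.0 | 4.8 / 1.2 | 4.8 / 0.8 |
| 1.01 | 4.5 / 0.5 | 5.0 / 0.5 | 3.7 / 0.5 |
| 1.11 | 21.2 / 6.8 | 4.0 / 0.7 | 5.2 / 1.5 |
| 1.22 | 61.2 / 38.3 | 5.3 / 0.8 | 4.5 / 0.8 |
| 1.11, mean units 3 and 1 (about 1,015 transfused) | 39.2 / 17.0 | 5.7 / 1.3 | 5.2 / 0.8 |

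The simulation error at a true 5% is √(0.05·0.95/600) ≈ 0.9 points. At 1.11 per unit the average spurious odds ratio is about 1.06 per 7 days of oldest-unit age. The correlation of oldest-unit age with units is about 0.43.

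**Sensitivity to unit counts.** Other assumed unit counts, with the SAP covariates, gave 9–20% at 1.11, about 5% at 1.01 and 26–62% at 1.22. Counts built from the Hb tiers in Protocol X, adjusting for arm and Hb only, gave 8–11% at 1.11 and 20–47% at 1.22. Adding units gave about 4–6% throughout.

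**Alpha.** For the composite, 0.05/0.01 = 5. Summed over the three outcomes for one exposure definition, the protocol spends 3 × 0.01 = 0.03 and the SAP 0.05 + 0.01 + 0.01 = 0.07. If the tests were independent: 1 − 0.99³ = 0.0297 against 1 − 0.95·0.99² = 0.0689.

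**The case against.** - *Mean age is already planned and serves as a check.* This stands. A reader might infer that all the age-of-blood models confuse dose with storage; the mean-age models do not do so mechanically.
- *Nadir Hb stands in for dose, because transfusion is triggered by Hb.* Partly. In a check at 1.11 per unit, adding nadir Hb cut the error at 5% from 20% to 12.5% with Poisson unit counts, and from 26% to 17% with overdispersed counts. Inflation remained.
- *The odds ratio of 1.11 is weak evidence.* This stands. Its p-value of 0.025 missed that study's own level of 0.0125. The study covered operations for PAD and used death or ACS within 30 days, not this trial's composite. At the lower limit, 1.01, there is no inflation. The documents give no per-unit odds ratio for wound infection or pneumonia.
- *Units may follow the outcome.* Bleeding or MI can prompt further transfusion, so total units is not a clean covariate. This stands and shapes the fix; the preliminary study in Protocol II counted units given before the event. Oldest-unit age has the same timing problem.
- *The models are assigned to the full ITT set, where many have no blood age.* A reader might infer that untransfused participants would be analysed with an invented value. Nothing in the SAP says so; records with no blood age would drop out of the fit. This needs a sentence, no more.
- *The SAP's 0.05 looks deliberate.* It matches the 95% interval in Table 24 and the 0.05 used for the Cox model of the primary endpoint. A reader might infer that 0.01 is the correct level; the documents show only that the two differ. The opening pages of the SAP were not in the copy available, so a record of the change there cannot be excluded.

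**Conclusion.** The point holds in a limited form. The oldest-unit models lack a term for number of units and can report a dose association as a storage effect. At nominal 5% the error is about 9–21% at 1.11 per unit (39% in the one setting with heavier transfusion), about 5% at 1.01 and roughly 20–60% at 1.22. These figures rest on assumed unit counts and on storage age being uniform and independent of dose. The direction and the remedy are firm; the exact size is not.

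A reader might infer that the plan will report a false storage effect. It does not follow: at 21%, about 79% of trials with no storage effect would still report none. The protocol's 0.01 level would not cure the problem either, since the error there was 6.8% at 1.11 in the main setting.

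The alpha for the composite is a plain difference between the documents. Both matters concern analyses listed under other analyses and leave the primary, secondary and safety analyses as they are.

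**What to change.** 1. Add number of units as a covariate in the oldest-unit models and as a row in Tables 24–26. Count only units given before the outcome event, and compute oldest and mean age from those same units. Say whether units given before randomisation count, and over which window units are counted in participants without the event, so that the two groups are treated alike.
2. Name mean age as the main exposure and oldest unit as supportive.
3. State that these models include transfused participants only, within each analysis population.
4. State one alpha for the composite. If it stays at 0.05, record it in the SAP as a departure from the protocol, as Protocol XVI.H requires; if it returns to 0.01, change the interval in Table 24 to 99%.

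The cost is one covariate from data already recorded, three table shells and a few sentences, best settled before database lock. Event timing is already needed for the time-to-event analyses of the primary and infectious endpoints in SAP 7.4.

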
Survival analysis techniques will be used to analyze the time-to-event data for the primary and major secondary endpoints. Kaplan-Meier analysis will be used to estimate the survival (not experiencing event) over time in the two intervention groups and a log-rank statistic will be used to test the equality of the survival function estimates in the two groups. Cox's Proportional Hazards models will be used to test the effect of the intervention on the time until endpoint events adjusted for age, RCRI, nadir Hb, site, and the interaction terms as described in the primary and secondary endpoint analyses. The analyses will be done on the ITT, mITT, No-Recent-Transfusion, Completers, and Per Protocol populations.

TABLE 4: Statistical Analysis Schema

Analyses	Statistical Methods	SAS Procedures
Primary Endpoint Composite endpoint at 90 days (Including all cause post-randomization mortality, MI, coronary revascularization, stroke, and acute renal failure)	1. Pearson chi-square 2. Logistic regression adjusted for Age, RCRI, Nadir Hb, Site, and the Interaction terms	1. PROC FREQ 2. PROC GENMOD
Secondary Endpoints 1. Composite endpoint of infectious complications at 90 days (wound infections, pneumonia, sepsis) 2. Composite endpoint of cardiac complications at 90 Days (arrhythmia, CHF exacerbation, cardiac arrest) 3. All-cause mortality after one year 4. Composite endpoint at 30 days (Including all cause post-randomization mortality, MI, coronary revascularization, stroke, and acute renal failure) 5. Length of hospital stay	For Binary Endpoints: 1. Pearson chi-square tests 2. Logistic regression adjusted for Age, RCRI, Nadir Hb, Site, and the Interaction terms For Length of Hospital Stay: 1. Wilcoxon test 2. Quantile regression adjusted for Age, RCRI, Nadir Hb, Site, and the Interaction terms	1. PROC FREQ 2. PROC GENMOD 1. PROC NPAR1WAY 2. PROC QUANTREG
Tertiary Endpoints 1. All cause post-randomization mortality at 90 days 2. Post-randomization MI at 90 days 3. Post-randomization coronary revascularization at 90 days 4. Post-randomization stroke at 90 days 5. Post-randomization acute renal failure at 90 days	For All Tertiary Endpoints: 1. Pearson chi-square tests 2. Logistic regression adjusted for Age, RCRI, Nadir Hb, Site, and the Interaction terms	1. PROC FREQ 2. PROC GENMOD

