4.5. Sample Size Consideration

The sample size estimation and power analysis are based on the hypothesis testing of the primary composite endpoint of all-cause post-randomization mortality, myocardial infarction (MI), coronary revascularization, acute renal failure, or post-randomization stroke up to 90 days after randomization. The primary hypothesis of the study is that in VA patients with high cardiac risk undergoing a surgical procedure, a significantly smaller proportion of participants receiving blood under a liberal transfusion strategy will experience the composite endpoint compared to participants under restrictive transfusion strategy at 90 days after randomization. The primary analysis will be done as an "intent-to-treat" analysis. Our database review revealed that 29.8% out of 25,343 patients in the VA population who were at high cardiac risk and had nadir postoperative Hb range between 6-9 gm/dl developed the composite endpoint of death, MI, acute renal failure, or coronary revascularization within 90 days from the index operation. Based on the analysis, a baseline event rate of 30% for the composite endpoint is expected in the restrictive group. We also assume a 25% reduction or 22.5% event rate in the liberal group. To detect the expected 7.5 percentage point difference or 25% reduction, a sample size of 1444 will be required at 90% power, 5% type-I error rate and with a two-sided test (Appendix 3). Assuming 5% dropout rate, then 1520 participants (or 760/group) will be needed to achieve the desired testing power.

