Tables 26a-e. Effect of Age of Blood Transfused on 90-day Pneumonia (ITT, mITT, No-Recent-Transfusion, Completers, Per-Protocol)

Factors	Coefficients	p-Values (Wald test)	OR (99% C.I.)
Using oldest unit transfused			
Age of Blood Transfused			
Liberal vs Restrictive			
Baseline Age of Participant			
RCRI			
1			
2			
3			
4			
Nadir Hb			
Using mean age of all the units transfused			
Age of Blood Transfused			
Liberal vs Restrictive			
Baseline Age of Participant			
RCRI			
1			
2			
3			
4			
Nadir Hb			

Table 27a-e. Cox Regression Model for Primary Endpoint (ITT, mITT, No-Recent-Transfusion, Completers, Per-Protocol)

Factors	Coefficients	S.E.	p-Values (Wald test)	HR (95% C.I.)
Liberal vs Restrictive				
Age				
RCRI				
1				
2				
3				
4				
Nadir Hb				

Table 28a-e. Cox Regression Model for Secondary Endpoints (ITT, mITT, No-Recent-Transfusion, Completers, Per-Protocol)

Factors	Coefficients	S.E.	p-Values (Wald test)	HR (99% C.I.)
90 Day Infectious Complications				
Liberal vs Restrictive				
Age				
RCRI				
1				
2				
3				
4				
Nadir Hb				
90 Day Cardiac Complications				
Liberal vs Restrictive				
Age				

Factors	Coefficients	S.E.	p-Values (Wald test)	HR (99% C.I.)
RCRI				
1				
2				
3				
4				
Nadir Hb				
30 Day Composite Rate of All-cause Postoperative Mortality, MI, Coronary Revascularization, Stroke, or Acute Renal Failure				
Liberal vs Restrictive				
Age				
RCRI				
1				
2				
3				
4				
Nadir Hb				
1 Year All-cause Mortality				
Liberal vs Restrictive				
Age				
RCRI				
1				
2				
3				
4				
Nadir Hb				

Table 29. Cumulative SAE Incidence by Treatment Group using MedDRA Coding in Randomized Participants, by Body System and Preferred Term (Safety)

	Liberal Arm (n=)			Restrictive Arm (n=)			All Subjects (N=)		
	Participants			Participants			Participants		
Body System and Preferred Term	N	(%)	Events	N	(%)	Events	N	(%)	Events
All Serious Adverse Events									
Infections and infestations									
Wound infection									
Sepsis									
... and so on									

Table 30. List of SAEs where Death of Randomized Participant Is Indicated (Safety)

Center	Ppt	Intervention Group	1. Start Date (date the SAE began)	Date of Death	Original SAE Attribution to Study	Detailed description of event
...						

Table 31. Summary of Laboratory Assessment (Safety)

Time	Assessments	Statistics	Liberal Arm	Restricted Arm	All Subjects
------	-------------	------------	-------------	----------------	--------------

			(n = ?)	(n = ?)	(N = ?)

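### Kaplan-Meier is planned for the 90-day infectious and cardiac composites, which exclude death, with no competing-risk method; if deaths are censored, the curves overstate incidence by a modest amount.

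*SAP*

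**What the plan says.** SAP 7.4 plans a supportive time-to-event analysis in which the "Kaplan-Meier method will be used to estimate the survival (not experiencing event) over time in the two intervention groups". Of the log-rank comparison the section says: "will be used to compare the survival functions in the two groups for the primary endpoint and the secondary endpoints using PROC LIFETEST". Adjusted Cox models are planned as well. Protocol XVI.E.5 carries the same plan: "Kaplan-Meier analysis will be used to estimate the survival (not experiencing event) over time in the two intervention groups".

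The shell for SAP Table 28a-e shows which secondary endpoints are meant. It lists "90 Day Infectious Complications", the 90-day cardiac composite, the 30-day composite and one-year mortality. SAP 3.2.2 defines the infectious composite as wound infection, pneumonia or sepsis. It defines the cardiac composite as treated new arrhythmia, heart failure exacerbation or cardiac arrest, and counts an arrest only if it is reversed; an arrest that is not reversed is recorded as a death. Neither composite therefore contains death.

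Neither document says whether a participant who dies without the event is censored at death, carried event-free to day 90, or treated as having had a competing event. Neither mentions a cumulative incidence function.

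The main analysis of both composites is a Pearson chi-square test on proportions (SAP 7.2, Tables 18a-e), followed by logistic regression (Tables 19a-e), at an alpha of 0.01.

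**The concern.** A participant who has died can no longer develop pneumonia or an arrhythmia. Kaplan-Meier with censoring at death treats that participant as if still able to have the event later, so one minus the curve estimates incidence in a hypothetical setting without death. It is higher than the proportion of randomized participants who have the event, so the same report would show one figure in Table 18 and a larger one on the curve.

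This matters more here than in a low-mortality trial. Protocol Table 2 reports deaths in 15.3% of high-risk patients with nadir hemoglobin 6-9 gm/dl and in 6.9% of those with 9-10 gm/dl, the two groups the protocol uses to stand for the restrictive and liberal arms. The tertiary hypothesis predicts fewer deaths under the liberal strategy. If mortality does differ, the overstatement differs too. At equal true incidence it makes the restrictive arm look worse on non-fatal complications, which is the direction of secondary hypotheses 1 and 2.

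**Working it through.** **The plan's own figures.** The documents give no incidence for either composite and no Kaplan-Meier figure to reproduce. The sample-size statement ("a sample size of 1444 will be required at 90% power, 5% type-I error rate and with a two-sided test") does reproduce, at 722 per arm and 1444/0.95 = 1520, but it concerns the primary composite and does not bear on this point.

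**Inputs.**
- D, total 90-day mortality: 15.3% and 6.9% (Protocol Table 2), and 4.2% and 2.6% (cardiac-surgery trial cited in Protocol I).
- F, true 90-day incidence of the composite: assumed equal in both arms at 15%, 20% or 25%. These values are assumptions.
- Constant hazards over the 90 days, also assumed.

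**Formulas.** With 90 days as the time unit, the death hazard is d = -ln(1 - D). The event hazard h is solved from

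F = h/(h + d) x [1 - exp(-(h + d))],

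which is the cumulative incidence with death competing. Kaplan-Meier with deaths censored then shows 1 - exp(-h).

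**Worked case, F = 20%.**
- D = 15.3%: d = 0.1661 and h = 0.2438. Check: 0.2438/0.4098 x (1 - exp(-0.4098)) = 0.5948 x 0.3362 = 0.200. Kaplan-Meier shows 1 - exp(-0.2438) = 21.6%.
- D = 6.9%: d = 0.0715 and h = 0.2319. Check: 0.7643 x 0.2617 = 0.200. Kaplan-Meier shows 1 - exp(-0.2319) = 20.7%.
- The gap is 0.9 points, although the true incidence is 20% in both arms. A simulation with 400,000 per arm agrees: crude 20.1% against 21.7% by Kaplan-Meier at D = 15.3%, and 20.0% against 20.7% at D = 6.9%.

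**Range.**

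| True incidence, both arms | Shown at D = 15.3% | Shown at D = 6.9% | Spurious gap | Shown at D = 4.2% | Shown at D = 2.6% | Spurious gap |
|---|---|---|---|---|---|---|
| 15% | 16.2% | 15.5% | 0.7 | 15.3% | 15.2% | 0.1 |
| 20% | 21.6% | 20.7% | 0.9 | 20.4% | 20.3% | 0.2 |
| 25% | 27.0% | 25.9% | 1.2 | 25.5% | 25.3% | 0.2 |

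Gaps are taken before rounding. The relative overstatement hardly depends on the event rate: about 1.08 at D = 15.3%, 1.035 at 6.9%, 1.02 at 4.2% and 1.01 at 2.6%.

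**Timing.** Constant hazards lie between two extremes. If every death came before any event, 20% would read 0.20/(1 - 0.153) = 23.6% and 0.20/(1 - 0.069) = 21.5%. If all deaths came late, the overstatement would go to zero.

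**The case against.** The strongest case against has four parts.

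*The documents do not say that deaths are censored.* This is correct. A reader might infer that the SAP prescribes it, but it is silent. If deaths were carried event-free to day 90, one minus Kaplan-Meier would equal the crude proportion and nothing would be overstated. What stands is that censoring is the usual default for an endpoint without death, and that the rule is unstated.

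*Only a descriptive display is affected.* This also stands. The chi-square and logistic analyses do not use Kaplan-Meier, and Table 18 gives the crude proportions. A reader might infer that the log-rank and Cox results are biased too. They are not: with deaths censored they remain valid comparisons of cause-specific hazards, though not of cumulative incidence. Appendix 5 lists no shell for a Kaplan-Meier figure, so the curves are planned in the text only.

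*The size depends on the mortality contrast.* Table 2 gives observational rates by nadir hemoglobin, with a relative difference of 1 - 6.9/15.3 = 55%. They are not a forecast of mortality by arm. For the primary composite the plan assumes much less ("We also assume a 25% reduction or 22.5% event rate in the liberal group"). Applying a 25% reduction to mortality instead, as an assumption, gives 15.3% vs 11.5% and gaps of about 0.3, 0.4 and 0.5 points at 15%, 20% and 25% incidence. A reader might also enter the Table 2 rates as probabilities of dying before any event, which gives gaps of 0.8-1.4 points. They are total mortality, which includes deaths after an infection or cardiac event, so that range is too high. For scale, at 20% incidence with 760 per arm the standard error of the arm difference is sqrt(2 x 0.20 x 0.80/760) = 2.05 points, and the artefact at that incidence (at most 0.9 points) is less than half of it.

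*The arm with more deaths is not always overstated more.* This is right as a limit. The statement holds at equal incidence. In absolute points it can reverse if that arm has clearly fewer events: 15% incidence with 15.3% mortality gives +1.2 points, while 30% with 11.5% gives +1.75.

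**Conclusion.** The point holds in a conditional and limited form. Kaplan-Meier is planned for two composites that exclude death, in a population with substantial mortality, and no competing-risk method is named. If deaths are censored, the curves overstate the proportion affected and will disagree with Table 18. At equal true incidence of 15-25%, constant hazards and equal follow-up, the false difference between arms is about 0.7-1.2 points under Table 2 mortality and 0.1-0.2 points under the cited cardiac-surgery trial's mortality.

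The incidences are assumed, and the result also depends on when deaths occur. The documents do not support a reading in which the secondary conclusions are unsafe or the restrictive arm must look worse. The primary composite, the 30-day composite and one-year mortality all include death and are not affected. This is a minor improvement to a supportive analysis, worth making because it is so cheap.

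**What to change.** In SAP 7.4, for the 90-day infectious and cardiac composites only:
- state that death without the event is a competing event;
- report Aalen-Johansen cumulative incidence by arm instead of Kaplan-Meier, so that with complete follow-up the day-90 value agrees with Table 18;
- label the log-rank test and the Table 28 Cox hazard ratios for these two endpoints as cause-specific. If a formal comparison of incidence over time is also wanted, name Gray's test or a Fine-Gray model in advance.

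Keep Kaplan-Meier for the primary composite, the 30-day composite and mortality. Record the change as a clarification of Protocol XVI.E.5.

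The cost is a PROC LIFETEST option and a few sentences of SAP wording. Death is already collected, so no new data are needed, and the primary analysis and sample size do not change.
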